6.1. Does the study involve the recruitment of participants?

No: If no, skip to 7.1

Yes: If yes; indicate how, when, where, and by whom participants will be recruited

Recruitment of participants into the study will be conducted by NFP program staff, including Outreach Specialists, Nurse Supervisors, and Nurse Home Visitors at the implementing agencies. Outreach Specialists are study-specific staff who will conduct outreach with community stakeholders, build awareness of the program, assess client eligibility, conduct the informed consent process, administer the baseline survey, and randomize participants throughout the study enrollment period.

Nurse Supervisors & Nurse Home Visitors are program staff that implement NFP and will also complete these study activities as they build their caseload.

NFP has existed in South Carolina for 7 years, and has existing relationships with many service providers in the community. Women can be referred to the NFP program through a variety of channels including, but not limited to: health care providers, WIC clinics, schools, pregnancy testing clinics, other home visiting programs, NFP clients or graduates, and Medicaid. Some clients are also “self-referred.” NFP aims to partner with these referral sources, as well as with community-based organizations and other agencies serving high-risk pregnant clients, to identify and engage women who may be eligible for the program. Methods for recruiting participants broadly fall into one of four categories:

- a) Information about a potential participant is submitted to NFP implementing agencies through the existing referral process, or she reaches out to NFP. The NFP Outreach Specialist will verbally assess whether the eligibility criteria are met and then schedule an in-person meeting for obtaining informed consent and completing study enrollment.
- b) A woman meets with an Outreach Specialist or Nurse Home Visitor who is stationed at a referral site (e.g. at a high volume prenatal care or WIC site), and can immediately consent to enroll in the study, if eligible.
- c) A potential client submits her information to a centralized website or phone number dedicated to the trial. Outreach staff will then contact the woman by phone to determine eligibility, and schedules an in-person meeting to obtain informed consent and complete study enrollment.
- d) South Carolina Department of Health & Human Services (SCDHHS) will provide a list of women who are newly enrolled in Medicaid and pregnant to NFP on a regular basis. NFP will send one letter to each mom newly enrolled in Medicaid letting her know that she may be eligible to participate in a no-cost, confidential study for a chance to receive a home nurse. The letter will not disclose that the study is for first-time moms, in case the letter is intercepted by someone other than the mom. Outreach staff will then contact these potential clients over the phone to describe the study, determine whether these clients are interested in the program, and schedule an in-person meeting. During the in-person meeting, a trained nurse will make the final eligibility determination and conduct study enrollment.

Throughout the enrollment period, three full-time Outreach Specialists will spend 3- 4 days per week at high-volume referral sites engaging clients and conducting study enrollment, as described in b) above. Nurse Home Visitors (NHVs) will also spend time at referral sites enrolling clients, while they build their caseloads.

6.1.1 Recruitment of nurses for nurse survey

Recruitment of nurses will be conducted by the research team, as well as nurse supervisors and their staff.

6.2. Are there any materials that will be used to recruit participants, e.g., emails, posters, and scripts?

No Yes: If yes; provide a list of the materials (also include copies with the application)

A community outreach campaign will be implemented in South Carolina to raise awareness of NFP services. Strategies will include advertisements in social media outlets and local media outlets, such as community newspapers. Outreach posters and flyers will also be placed throughout targeted neighborhoods in strategic venues (e.g., laundromats, bodegas, markets, etc.). Radio and television advertisements (using the same script) will also be utilized to raise awareness of NFP services. These advertisements will allow interested applicants to find out more about the study through a centralized website and phone number dedicated to the trial, which will be managed by NFP Outreach Specialists.

An Enrollment Script will be used by NFP program staff to recruit participants for the program, explain the study and determine eligibility.

For those prospective study participants who miss their scheduled study enrollment visit, the NFP program staff will call the mom to reschedule and send a letter in the mail, as follow-up. (See Survey Reschedule Letter).

6.2.1. Strategies will include sending emails to Nurse Supervisors with suggested email templates to send to their current and former staff to complete the survey. The research team may also send emails to recruit current and former staff.

7. Available Resources

7.1. Describe the feasibility of recruiting the required number of participants within the recruitment period

NFP currently restricts outreach due to limited slots available for new clients. Once the study starts, NFP is confident that the combination of existing referral sources, new outreach strategies, active outreach at referral sites, and outreach to recent Medicaid enrollees will enable the project to recruit the required number of eligible participants per year (n=1,000). NFP currently serves about 800 first-time mothers per year in the same communities that will participate in the study. The study will necessitate that NFP scale up by 25%, which NFP is committed to doing by allocating staff (leadership and project personnel) and marketing resources to increase referrals.

Community organizations that have existing relationships with target families will introduce clients to NFP, acting as a trusted intermediary. Referral networks will also be created through engaging managed care organizations (MCOs), hospitals, Federally Qualified Health Centers, and large physician groups to ensure a robust referral pipeline. Furthermore, agencies outside of the healthcare arena at the local and state level have become referral sources for NFP programs in South Carolina. For example, in Anderson, SC, the Office of the Solicitor (District Attorney) is such a partner, as is the Office of First Steps to School Readiness, whose board of directors consists of top-level decision-makers within state departments and agencies (e.g. Department of Health & Human Services, Department of Social Services, etc.).

7.2. Describe how the Principal Investigator will ensure that a sufficient amount of time will be devoted to conducting and completing the research.

The Principal Investigator is committed to dedicating a sufficient amount of time to conduct and complete the research. She has a demonstrated track-record of conducting and completing large-scale research studies, particularly those that have a long time horizon. The team is actively pursuing additional funding to cover a substantial share of the PI's time.

7.3. Are there research staff members, in addition to the Principal Investigator?

No: If no, skip to 7.5

Yes: If yes; outline training plans to ensure that research staff members are adequately informed about the protocol and study-related duties

All research and program staff who will have direct interaction with participants and/or access to identifiable information will review Harvard's Human Research Protection Program Plan as part of their initial orientation and will complete (and regularly renew) Harvard's online training curriculum available through the CITI program. In addition, all program staff who are conducting study enrollment will receive a minimum of eight hours of training by evaluation staff on the protection of human subjects and the foundations of the experimental design. Specifically, program staff who are responsible for enrolling eligible applicants in the study will be trained in obtaining informed consent, administering the baseline survey, explaining random assignment, protecting participants' privacy and

confidentiality, and reporting adverse events. We will train the program staff using IRB-approved protocols, scripts, consent forms and survey instruments.

7.4. Describe the minimum qualifications for each research role (e.g., RN, social worker) their experience in conducting research, and their knowledge of local study sites and culture

Outreach Specialists will have at least a high school diploma plus a substantial amount of college coursework. Outreach Specialists will receive training in research, ethics and study protocols. These individuals will have a strong understanding of the local landscape and culture, customs and norms, including how to communicate effectively with formal and informal leaders of the communities being served through the project. The Outreach Specialists already on staff have existing relationships in local communities, and can activate those relationships for the benefit of the project. They also possess the skills to engage new partners and cultivate new relationships. Additionally, many Outreach Specialists have backgrounds in community development and community organizing.

Nurse Supervisors will be registered nurses (RNs) who manage the Nurse Home Visitors. At each agency, they will play a role in outreach and recruitment, managing referrals, and, in some cases, enrollment of subjects. Supervisors will have a deep knowledge of the agency they work for and the community served. Ten such supervisors already have experience managing NFP at their agency. One new supervisor will be hired for this project. This role requires a minimum BSN and preferred master's preparation in nursing or a related field.

Nurse Home Visitors will also be RNs with a Bachelor of Science Degree in Nursing who have a very strong knowledge of the study sites. The majority of the nurses already on staff have prior experience implementing the NFP program at the study sites, and several of them have been implementing the program since 2008 when NFP began implementation in South Carolina. Seventeen new nurses will also be hired for this project. These individuals will receive training in research, ethics and study protocols and may have past experience conducting research. A majority of the nurses are residents of the communities being served, and have a background in serving those communities prior to coming to NFP.

Nurse Supervisors and Nurse Home Visitors are trained to screen for various abuses (including substance abuse and domestic violence) and to make referrals to local support services. They are also mandated reporters in the state of South Carolina. As mandated reporters, they must report to the appropriate authorities when they have reason to believe, in their professional capacity, that a child has been abused or neglected.

7.5. Briefly describe how the research facilities and equipment at the research site(s) support the protocol's aims, e.g., private rooms available for interviews, etc.

NFP program staff who are conducting study enrollment at the NFP implementing agencies will be provided private rooms to conduct interviews, and secure tablets with encrypted survey forms to collect baseline data and randomize participants.

For clients who are approached at referral sites, NFP staff may initially engage clients in a public space (e.g. the waiting room at a health clinic or a table at a WIC clinic). Study staff will secure private space for obtaining informed consent and conducting interviews. In some instances, the study consent process and baseline interview may be completed in a follow-up meeting at an agreed upon location, such as the woman's home or another neutral, private location.

NFP staff will be provided with a toll-free number that they can call to reach the core research team to ask questions or report adverse events. This toll-free number will be monitored during standard

business hours. NFP staff will also be provided with an email address ([contact]) that is dedicated to this study and monitored on a regular basis.

7.6. Are there provisions for medical and/or psychological support resources (e.g., in the event of incidental findings, research-related stress)?

No Yes: If yes; describe the provisions and their availability

There is limited risk of research-related stress. However, NFP program staff are registered nurses trained to provide resources/referrals to help pregnant women deal with stress.

7.6.1 Nurse survey: Are there provisions for medical and/or psychological support resources (e.g., in the event of incidental findings, research-related stress)? Yes, for nurses who are currently employed by NFP.

There is limited risk of research-related stress. However, if current NFP nurses experience stress as a result of the survey, their organizations already have systems in place for nurses to bring any thoughts, questions, or concerns that may come about by the research. These resources and support systems include, but are not limited to, case conferences, reflective supervision, team meeting education modules, and employee assistant programs which are available at many sites. We provide information about resources and support systems in the consent form and encourage nurses to reach out to their nurse supervisors and colleagues if they need information on how to access these services. We also inform nurses that they can contact the research team directly if they do not know who to contact, or do not feel comfortable contacting someone at their site directly.

These resources and supports are not necessarily available to former NFP nurses and are not included in the consent form for former NFP nurses.

2. Vulnerable Populations

2.1. Are there any potentially vulnerable populations (e.g., children, pregnant women, human fetuses, neonates, prisoners, elderly, economically disadvantaged, employees or students of the investigator or sponsor, undocumented, terminally ill, cognitively impaired or mentally ill, etc.)?

No: If no, skip to 3.1

Yes: If yes; identify all vulnerable populations

Pregnant women, neonates, children

2.2. Describe safeguards to protect their rights and welfare

This research study involves no more than minimal risk to pregnant women and their children. The research is designed to evaluate a service program that is designed specifically to provide additional resources to these populations, which is why enrollment focuses on them. Information on children will be obtained from administrative data and only with their mother's written informed consent.

Nurse Supervisors and Nurse Home Visitors are trained to screen for various abuses (including substance abuse and domestic violence) and to make referrals to local support services. They are also mandated reporters in the state of South Carolina. As mandated reporters, they must report to the appropriate authorities when they have reason to believe, in their professional capacity, that a child has been abused or neglected.

If the mandated reporter has reason to believe that a child is being abused or neglected by a parent, guardian or person responsible for a child's welfare, reports must be made to the Department of Social Services (DSS) office or law enforcement agency in the county in which the child resides.

If the mandated reporter has reason to believe that a child is being abused or neglected by someone other than a parent, guardian or person responsible for a child's welfare, reports must be made to a law enforcement agency in the county in which the child resides.

The nurses will comply with state laws that require them to report if they have reason to believe a child is being abused or neglected.

3. Consent Process

3.1. Will consent to participate be obtained?

No: If no, skip to 3.5

Yes: If yes; describe the setting, role of individuals involved, timeframe(s), and steps to minimize coercion/undue influence during the consent process (at the time of initial consent and throughout the study)

NFP program staff will be trained by the study team about how to implement the informed consent process. To minimize coercion/undue influence, program staff will allow the participant as much time as she needs to read through the consent form and will also review the consent form with her verbally (estimated time: 10-15 minutes). The program staff will emphasize that participation in the study is voluntary, and that participants may refuse to answer questions or may choose to stop participating in the study at any time. Program staff will be trained to check for participant's comprehension of what it means to be in the study (particularly their understanding of the random assignment process) and will encourage study participants to ask questions now and in the future, if they have them.

Based on the local population in South Carolina, the majority of participants will speak English as their primary language. The consent materials will also be translated into Spanish (see Translation Attestation Form attached). Occasionally, participants may speak another language besides English or Spanish, but based on existing enrollment patterns we expect this to be less than 0.5% of cases. In those rare cases, NFP program staff will utilize an interpreter service through the health care center where they work to facilitate the informed consent process.

Due to COVID-19, informed consent will be obtained virtually over the phone. Nurses are trained in motivational interviewing and will continue to check for participant's comprehension of what it means to be in the study, the understanding of the randomization process, and encourage questions. Written informed consent will be waived during this period and up until in person study visits are possible.

3.2. Are there any special populations?

No Yes: If yes; describe the process to obtain consent, permission or assent

NFP currently targets its services to vulnerable young mothers, including pregnant minors (under 18 years old), who have the highest need of support during their pregnancy and first years as a parent. The use of Medicaid funds to cover NFP for the expansion population in South Carolina is predicated on an evaluation of its effects using this randomized controlled design. The study is the only pathway through which anyone who meets the inclusion criteria in South Carolina, including pregnant minors, can access NFP.

South Carolina law does not require parental consent for minors to seek healthcare services, including reproductive healthcare services. In accordance with this law, and to protect the well-being of the young mothers who may be endangered if they are required but not able to obtain parental permission, it is necessary to allow an avenue for pregnant minors to provide their own consent to participate in the study. If pregnant minors were not allowed to provide their own consent, and were thus excluded from study enrollment if they could not practicably obtain parental consent, this would deny them access to Medicaid-funded NFP services – which would be inconsistent both with the goals of

providing additional resources to this vulnerable population and with the laws and regulations in South Carolina. (Currently, the median age of pregnant women who receive NFP services in South Carolina is 19, meaning that a substantial share of those served are minors.³)

NFP staff are trained to communicate and provide care to this special population of pregnant minors, and will be implementing the informed consent process with them. During the consent process, NFP staff will take special care to make sure that each pregnant minor understands that her participation in the research study is voluntary and that she can quit at any time without penalty.

NFP staff will invite each pregnant minor to provide an electronic signature if she wishes to participate in the study. The pregnant minor's electronic signature will provide a permanent record of 1) the information conveyed to the mother about the study, 2) the fact that the consent process occurred, and 3) the mother's willingness to participate. By default, NFP staff will not provide pregnant minors (under 18) with a copy of the unsigned consent form, in case her family does not yet know she is pregnant. Instead, NFP staff will provide pregnant minors with the Principal Investigator's email address ([contact]) and/or the IRB's toll-free number ([name]) in case she later has questions, concerns or complaints about this research study.

However, if a participant under 18 years old actively asks for a copy of the unsigned consent form, or if a guardian who is present at the time of study enrollment actively asks to keep a copy of the unsigned consent form, a copy of the consent form will be provided. In these situations, it is implied that the minor is willing to share the information about her pregnancy with her family. During the consent process, the nurse will remind the minor that she is free to discuss her decision to participate in the research with her family, friends, or doctors, but that she does not need her guardian's permission to participate in the study.

NFP nurses will comply with state laws that require them to report if they have reason to believe a child is being abused or neglected. During the informed consent process, NFP staff will make the participant aware that they are mandated reporters who are required to report to the appropriate authorities if they have reason to believe a child is being abused or neglected. They will explain to the participant that it is their legal and ethical responsibility to report situations of child abuse, child neglect, or any life-threatening situation to appropriate authorities.

3.3. Will consent of the participants be documented in writing?

Yes No: If no; describe the rationale for requesting a waiver or alteration of documentation of consent (and/or parental permission)

We will obtain an electronic signature from subjects who consent to participate. Due to COVID-19 we will waive written consent and only obtain verbal consent until in person study visits are possible.

3.4. Will participants be provided with a copy of their signed consent form or information sheet (when a consent form is not signed)?

Yes No: If no; explain any extenuating circumstances that make it impossible or inappropriate to meet this requirement, i.e., doing so may place participants at increased risk, if inadvertently disclosed

Participants 18 years or older will be provided a copy of the unsigned consent form/information sheet to take home that is identical to the one she signed, but does not include her signature. This will be done to protect the participant's privacy in the case where she inadvertently loses or misplaces the information sheet (because the version she has will not contain her name).

³ http://www.nursefamilypartnership.org/assets/PDF/Communities/State-profiles/SC_State_Profile.aspx

Participants under 18 years old will not be provided a copy of the unsigned consent form by default, to protect their privacy, safety and well-being. Providing information sheets to pregnant minors may put them at increased risk, particularly in cases where her family does not yet know she is pregnant. Instead, NFP staff will provide pregnant minors with the Principal Investigator's email address ([contact]) and/or the IRB's toll-free number ([name]) in case she later has questions, concerns or complaints about this research study. However, if a participant under 18 years old actively asks for a copy of the unsigned consent form, or if a guardian who is present at the time of study enrollment actively asks to keep a copy of the unsigned consent form, a copy of the consent form will be provided. In these situations, it is implied that the minor is willing to share the information about her pregnancy with her family. During the consent process, the nurse will remind the minor that she is free to discuss her decision to participate in the research with her family, friends, or doctors, but that she does not need her guardian's permission to participate in the study.

Due to COVID-19, a copy of the unsigned consent form//information sheet will be mailed to clients.

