applicant will be informed during the consent process that the interview may also be recorded for quality assurance purposes.

All eligible program applicants who provide their written consent and complete the baseline interview will be randomly assigned “on-the-spot” to a treatment group that is offered access to the NFP program or to a control group that is not offered the opportunity to enroll in NFP. Program staff will use a pre-programmed randomization function on their tablets to conduct the random assignment. Program staff will explain to the participant that the computer chooses which study group she will be assigned to, and that her assignment is not dependent on any personal traits or characteristics.

If the applicant is assigned to the control group, the program staff will explain that she was not chosen by the computer to receive NFP services, but that she may continue to seek care at the health care center as she normally would. The program staff will also provide a list of other resources and programs that are available in the community.

If the applicant is assigned to the treatment group, the program staff will proceed to schedule her first home-visiting appointment. The program staff will also provide treatment group members with a list of other resources and programs that are available in the community. In response to COVID-19, the materials the applicant would have otherwise received in person (copy of the consent form, \$25 gift card, and list of community resources) will be mailed to the address the applicant provides.

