Participants who enroll in the study will be provided with a \$25 gift card to compensate them for their time in completing the baseline survey, regardless of whether they are randomized to the treatment group or the control group. Due to COVID-19, gift cards will be mailed to clients to compensate them for their time for both treatment and control group.

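### The COVID-19 sentence closing Consent Process 3.4 mails the unsigned consent form to clients with no under-18 exception, which conflicts on its face with the no-copy default for minors

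*Protocol*

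**What the plan says.** The protocol's numbering restarts after section 7. Here 3.2, 3.4 and 3.5 mean the Consent Process part, 4.2, 4.4 and 4.6 the Study Design part, and other parts are named.

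- **The rule for minors.** Section 3.4 states: "Participants under 18 years old will not be provided a copy of the unsigned consent form by default, to protect their privacy, safety and well-being". Section 3.2 says the same, on the ground that the pregnancy may still be unknown at home: "By default, NFP staff will not provide pregnant minors (under 18) with a copy of the unsigned consent form, in case her family does not" (quotation cut short). Section 3.5 repeats it.
- **The reason.** "Providing information sheets to pregnant minors may put them at increased risk, particularly in cases where her family does not yet know she is pregnant".
- **The exceptions.** A copy is given only on request, by the minor or by a guardian attending enrolment: "if a participant under 18 years old actively asks for a copy of the unsigned consent form, or if a guardian who is present" (quotation cut short).
- **The COVID-19 sentence in 3.4.** "Due to COVID-19, a copy of the unsigned consent form//information sheet will be mailed to clients".
- **The COVID-19 sentence in 4.6.** Mailing replaces what the applicant would normally have been given face to face. A parenthesis names the copy of the consent form, the gift card and the resource list. The sentence ends "list of community resources) will be mailed to the address the applicant provides".

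**The concern.** The protocol identifies a specific harm, that paper evidence of study participation may reach a family unaware of a minor's pregnancy, and adopts a default to prevent it. A few lines later it introduces postal delivery of the same document without saying whether that default still applies. Minors are eligible from age 15 (4.4), and under 3.2 they may consent for themselves.

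Post can be opened by someone else in the household. The protocol recognises this in Recruitment Methods 6.1(d), where the letter to new Medicaid enrollees leaves out that the study is for first-time mothers for that reason. The COVID-19 mailing text has no comparable precaution, apart from the applicant supplying the address. What is at stake is the privacy and safety of the minors enrolled remotely. No endpoint, estimate or power figure depends on it.

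**Working it through.** There is no planned figure to reproduce. The check is a comparison of texts, with simple proportions for scale.

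**1. The texts side by side**

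| Place | Who gets the unsigned form | Age limit | Request needed for minors | Delivery |
|---|---|---|---|---|
| 3.2, 3.4, 3.5 (standing rule) | Adults by default (stated in 3.4); minors by exception | Yes, 18 | Yes: minor, or guardian present | In person |
| 3.4, closing COVID-19 sentence | Clients | None | None | Mailed, address not specified |
| 4.6, COVID-19 sentence | The applicant, in place of what she would have had in person | None | None stated; can be inferred | Mailed to the address she provides |

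The two paragraphs before the closing sentence of 3.4 separate participants aged 18 or older from those under 18. The closing sentence uses neither category. Read literally, it covers a 15- to 17-year-old who has not asked for a copy, and the standing rule says she should not receive one. No section states which text prevails.

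**2. Share of minors**

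SAP Addendum 4, Table 3 gives the under-18 counts among mothers with an index birth: 225 of 3,295 in the nurse home visiting group and 117 of 1,637 in usual care.

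(225 + 117) / (3,295 + 1,637) = 342 / 4,932 = 0.0693, or 6.9%.

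Table 1 of that addendum defines under 18 as a due date before the 18th birthday. Everyone counted was therefore a minor at enrolment, and anyone who turned 18 between enrolment and due date is left out. Within that sample, 6.9% is a floor for minors at enrolment.

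**3. How much remote enrolment there was**

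The documents give no number. Protocol 4.2 plans enrolment to July 2020, and SAP 1.6 dates the pandemic from March 23, 2020. SAP 3.3 gives the latest expected delivery date as November 7, 2020. Assuming the usual 280 days from last menstrual period to due date:

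- November 7, 2020 − 280 days = February 1, 2020, the latest last menstrual period in the study.
- On March 23, 2020 that woman was 51 days along, or 7 weeks 2 days.
- On July 31, 2020 she would have been 181 days along, or 25 weeks 6 days.

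Every other participant was at least as far along on each date. Had enrolment continued normally through July, it would have brought in women early in pregnancy. One enrolled on July 31 at 7 weeks 2 days would be due 229 days later, on March 17, 2021, and no due date is that late. Remote enrolment was therefore probably short or sparse.

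SAP 3.3 prints a wrong year for the end of its 120-day birth window: 120 days after November 7, 2020 is March 7, 2021, not 2020. The November date itself agrees with the later dates in that paragraph, since March 7, 2021 plus 24 months plus 6 months is September 7, 2023, as printed.

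**The case against.** The best reply is that the closing sentence of 3.4 follows directly after the rules on who is due a copy, so its natural meaning is that COVID-19 changed how a copy is delivered and not who receives one. Section 4.6 supports this: a minor would not by default have been handed the form, so there is nothing to mail in its place. She also chooses the address.

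Much of this stands. A reader might infer that the sentence sends the form to every client, that it cancels the safeguard outright, or that a minor's form would necessarily go to her parents' home. The documents support none of these. The text says clients, without more; a harmless reading exists; and the applicant supplies the address.

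The reply does not settle the matter. The limiting clause is in 4.6 and absent from 3.4. Even in 4.6 the parenthesis lists the consent form for the applicant with no age condition. Nothing tells staff to ask whether the address is private.

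A reader might also add the other mailed items, since Costs and Payments 10.2 says "gift cards will be mailed to clients to compensate them for their time for both treatment and control group". The under-18 rule covers only the consent form, and neither the gift card nor the resource list is described as revealing a pregnancy. They are not part of the contradiction.

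A further reply is that enrolment was due to end in July 2020, so a change protects few or none prospectively. That is fair. But version 20, dated 08/04/2022, still carries the sentence, and the documents do not record how minors were handled.

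**Conclusion.** The concern holds as an internal inconsistency on consent and privacy. The COVID-19 sentence in 3.4 has no under-18 exception and conflicts on its face with the default in 3.2, 3.4 and 3.5. Section 4.6 is narrower but does not resolve the conflict. A site following 3.4 literally could expose a minor to the harm the protocol names.

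The size is not known. The 6.9% (342 of 4,932) shows that minors were a real part of the sample, but applying it to an assumed number of remote enrolments would give a count the documents do not support, because the due-date evidence suggests few women were enrolled in that period. That inference rests on the November 7, 2020 date and the 280-day convention.

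Two further inferences should be resisted. The case for minors' own consent in 3.2 and 3.5 rests mainly on state law, on the danger to some minors if permission were required, and on the study being the only route to the programme; it does not rest on the no-copy rule. Nor do the documents show that any form was mailed to a minor or that a disclosure occurred, so enrolment under this text is not in itself a confidentiality event.

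**What to change.** - **Text.** Reconcile 3.4 and 4.6 with a sentence in each saying that the existing under-18 default also applies to mailed copies: no consent form is posted to a participant under 18 unless one of the existing request exceptions is met.
- **Records.** Check whether any consent forms were mailed to participants under 18 during remote enrolment, and whether a request was documented.
- **Reporting.** Refer any potential breach found to the IRB under Reportable Events 6.1, which leaves the determination to the IRB.

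The cost is a short amendment and a records check limited to minors enrolled remotely. No analysis, sample size or outcome definition changes.
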